In the pilot phase, we will determine the logistics of the training timing and schedule and establish pass/fail cut-off scores for acceptable competency. HCWs will sign standard written informed consent. The pilot phase will consist of the intervention training for 10 HCWs in HIV care at Kenyatta National Hospital. The training will take place over approximately 2-3 days and include didactic and role-playing experiences with the SPs. During the training, provider participants will rotate through up to 7 video-taped SP encounters. Each encounter will last approximately 10-15 minutes. During the encounter, the HCW will counsel the SP as if they were a real client. Encounters will be followed by facilitated group debriefing sessions. The trainer will facilitate discussion and each provider will have the opportunity to discuss their experience and receive feedback from peers and actors. Faculty experts will review and grade the videotapes via an online learning management system. A study team of faculty and experts from Kenya and the US with expertise in adolescent health will provide structured feedback on participants' technical competency according to a faculty checklist.

Training evaluation

At completion of the training session, all HCW participants will complete a training satisfaction survey and a competency survey. Due to COVID-19 pandemic starting March 2020, HCW surveys for Wave 4 will be conducted by phone instead of in-person at a healthcare facility. After the implementation period, about 5 HCWs will be invited to participate in brief exit interviews on relevance of the training to their work, and barriers and facilitators to implementing skills they learned. Exit interviews will be conducted by a study staff member in a private room and last up to 30 minutes.

7b. Stepped Wedge Randomized Controlled Trial (RCT)

We will conduct a stepped wedge randomized controlled trial (RCT) to test the impact of the finalized clinical training intervention on health seeking behaviors of HIV-infected adolescents.

Baseline assessment

At each of the enrolled clinics, we will conduct a baseline assessment of all clinical and satisfaction endpoints, including audits of adolescent client clinical records, and adolescent satisfaction surveys. Facility surveys will be conducted with a clinic representative to assess staffing, training experience, and current services for adolescent HIV care.

Intervention waves

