8. STUDY SCHEDULE

In this trial, there will be 4 waves of 6 clinics per wave, and 5 measurement periods, including baseline (Table 3). Total duration of the trial is approximately 3 years. Each wave will be rolled out approximately every nine months. Data pulls will occur 15 months after the HCW training, to ensure that all clients who present within the exposure time period have a full 6 months to return for care.

	Introduction of Intervention									
Clinic clusters	Baseline	Month 1	Month 10	Month 19	Month 28					
Wave 1: Sites 1-6	0	Х	Х	Х	Х					
Wave 2: Sites 7-12	0	0	Х	Х	Х					
Wave 3: Sites 13-18	0	0	0	Х	Х					
Wave 4: Sites 19-24	0	0	0	0	Х					

An overview of the anticipated overall study schedule for one wave is shown in Table 4, following page. The study will be conducted over five years. During year one, we anticipate script development, recruiting and training SPs, developing measurement checklists, and piloting initial encounters at Kenyatta National Hospital. During year two, we will recruit and randomize study sites, and begin implementation of the intervention. The intervention will be rolled out in waves, completing measurement and intervention cycles during year 4. Year 5 will be dedicated to statistical outcome analyses, cost effectiveness analyses and modeling, and dissemination of study findings both locally and internationally.

SPEED Protocol Protocol # Version 7.0 May 11 2020

Table 4. Overview of SPEED Study 2015 - 2020

	Y1		Y2			Y3			Y4				Y5							
	Q1	Q2	Q3	Q4																
Study Planning		1		I	1		I													
Protocol development																				
IRB Submissions																				
Implementation	r			1	1	ī	r	Ū	ī											
Site selection																				
Actor Training																				
Pilot phase																				
Consents & Randomization																				
Baseline OR EMR data pull					х				х				х				х	х		
Wave 1																				
Training																				
Exposure time & data pull (X)									Х											
Wave 2					Х															
Training																				
Exposure time & data pull (X)												Х								
Wave 3					Х															
Training																				
Exposure time & data pull (X)															Х					
Wave 4					Х															
Training																				
Exposure time & data pull (X)																		Х		
Post-trial data pull																			Х	
Analysis																				
Data Analysis																				
Dissemination	1	1		1			1													

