11. DATA COLLECTION

All data collection tools submitted with this application can be found in the Appendices.

Data sources for HCW participants

- Audio-visual recordings: Video-recordings, locally recorded on a web-camera and uploaded to the SPEED learning management system (LMS), will be made of each HCW-SP interaction for training, scoring, and debriefing/feedback purposes in the pilot and in the RCT. The LMS will utilize Canvas software, a program available only to the Study Team and HCW participants. Each HCW will have a study ID number assigned to them and will log in to the LMS using a user name and private password.
- Surveys:
 - Actor feedback checklist (used in training only): Actors will complete an actor feedback checklist and review it with each HCW during the training.
 - Faculty checklist (used in training only): Faculty experts will review the videos and complete a faculty checklist with a final competency score for each HCW immediately after the training. These scores will be stored with each user record.
 - HCW sociodemographic and satisfaction survey: HCW participants will complete the sociodemographic and satisfaction questions at baseline and in the SPEED training.
 - HCW self-rated competency: HCW participants will complete the competency survey immediately after their training and at the end of each wave to assess perceived competency to care for adolescent patients. The survey will be repeated to assess changes in competency over time during the trial. The final survey will be conducted by telephone due to COVID-19.
 - Exit interviews: A purposeful sample of HCW participants from each wave will take part in one semi-structured exit interview each at the end of the RCT to better understand barriers and facilitators to applying the skills they learned in the SPEED intervention to their routine practice. The interview will follow a structured interview guide.
 - Facility survey: This survey will be administered to a health facility representative at baseline and at the end of each wave of the RCT to capture facility characteristics, including turn-over of SPEED-trained HCWs, patient volume, and any relevant changes in HIV policies and procedures.
- Program records:
 - *Cost data:* Direct and indirect cost data for the CEA/CUA analyses will be obtained from clinic program data (e.g. HCW salaries from employment records)

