12. STATISTICAL CONSIDERATIONS

12a. Sample Size Considerations

For the Aim 2 RCT, we based our sample size and power calculations on the primary outcome of retention in care, obtained from EMR data. This outcome is binary on the individual level. We used the methods described by Hussey and Hughes [32] to determine power assuming an evaluation with 24 clusters and 5 time points (including baseline). We include 24 clinics in this study to account for the possibility that 15% drop-out without replacement. We assumed that only a small proportion of the 40 HIV-positive adolescents enrolled in HIV care per clinic may be newly enrolled or recently re-engaged in care. As such, we estimated the minimum number of records per clinic for 80% power to detect a 15% difference between control and intervention periods. We assumed a coefficient of variation (τ/μ) of 0.25 and calculated the power for a two-tailed test with α =0.05. Based on relevant published data [7], we assumed that 75% of adolescents in the control period will return to clinic after first visit. Under these assumptions, we estimate needing at least 5 adolescents per clinic. As such, the lower bound of the sample size required is estimated to be 720 clinic records (6 records/site X 24 sites X 5time points). If N=20

clinics are retained, we would need 7 adolescents per site, per time point, or a minimum of 700 records total.

In the optimal scenario with an average of 40 adolescents in care at each facility, our estimated analysis sample size would be at least 4,800 (5 time points). Under the same assumptions described above, we would have >99% power to detect a 15% difference in retention between the intervention and control periods.

We expect to have adequate power to detect an intervention effect for the analysis with a broader definition of retention in care (return for any follow-up visit within 6 months), because this is likely a more common pattern of follow-up than either return among newly enrolled or return after re-engagement in care.

12b. Planned interim analyses (if applicable)

Because this is a randomized trial with a stepped-wedge (staggered roll-out) design, there will be no interim analyses or stopping rules.

12c. Overview of analysis plan

Pilot phase

Qualitative feedback from participants, actors, and faculty experts will be used to finalize the case scripts, actor checklist, and HCW satisfaction survey.

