Data from the completed faculty checklists will be used to establish competency scores. Participants, faculty experts, and actors will be asked to provide qualitative feedback on the checklist indicators. Inter-rater reliability of the faculty checklist will be determined using Cohen's kappa. We will assess correlation of checklist variables and utilize principal component analysis to reduce the number of variables, using a scree test method to plot eigenvalues. Pass/fail cutoff scores will utilize relative and absolute standard-setting processes [33]. In relative processes, initial pass/fail determinations will depend on the performance of the cohort, such that all scoring less than 1 standard deviation below the mean receives a fail. Relative standards are useful with new trainings where there is no prior performance data. Subsequently we will explore standard-setting using an iterative combination of the Angoff item-based method and the Hofstee whole-test method. The Angoff method establishes the probability of a borderline student to accomplish each item on the checklist. The sum of probabilities across items is then equal to a passing score. A team review process is convened in which reviewers discuss outlier ratings, assess performance data after pilot testing, and revision of ratings if necessary. The Hofstee whole-test method combines normative and absolute judgments, in that checklist reviewers make four determinations: the minimum and maximum acceptable passing scores. and the minimum and maximum proportions of students failing. A final cut-off determination will be made by averaging the Hofstee and Angoff scores.

Stepped-Wedge Randomized Controlled Trial

The primary analysis will be an intent-to-treat (ITT) analysis, assuming that adolescents who receive care at clinics after the SPEED training will be 'exposed' to HCWs trained in the SPEED intervention until the end of the study.

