A CONSORT diagram, adapted for a stepped-wedge design [34] will be used to show the number of HCW-participants within clusters and flow of randomized stepped wedge clusters though the five time periods. We will report the number of clinics selected for inclusion, assignment to intervention or control at each time period, and the number of HCWs trained at each facility. We will report number of excluded clusters and any reasons for exclusion. No replacement will be used. Facility-specific information – adolescent patient volume, number of HCWs and presence of any adolescent-specific service (peer groups, clinics etc.) prior to the intervention – will be grouped by clinic and recorded. Baseline values of primary and process outcomes, and socio-demographic characteristics of adolescents and HCWs will be presented in a descriptive table.

We will use generalized linear mixed models (GLMM), which are more efficient than paired ttests and linear mixed models (LMMs) in the analysis of cluster RCTs when the size of clusters is unequal [32] to compare the probability of an adolescent returning to clinic after enrollment visit OR second visit after >3 months LTFU between the intervention and control periods [35]. To estimate the effect of the intervention (*Xij*) on the individual level, we will use a GLMM model with a Poisson distribution and robust standard errors, allowing for random effects for clusters (*ui*) and fixed effects for time (*j*). This approach models individual level outcomes, adjusts for temporal trends and accounts for correlation of outcomes within a cluster (clinic). We will estimate adjusted risk ratios (ARR), adjusted risk differences (ARDs) and 95% confidence intervals at the 5% significance level (two-sided). Adjusted risk ratios will be estimated for secondary outcomes: initiating and adherent to ART (≥80% in the dosing period by pharmacy records), 12-month retention in care; viral suppression (<100 copies/ml, <1000 copies/ml), and referred for ancillary services (family planning and TB screening). Models will be adjusted for facility type, patient volume, and exposure to prior adolescent health interventions (c).

The equation for a generic model is: $Y_{ijk} = \beta_0 + \beta j_{time} + \beta_{effect} X_{ij} + \beta c X ij$, $ui + \varepsilon ij$

- Analyses of process outcomes to understand intervention mechanisms will include:
 - Mean HCW competency (passing score proportion per clinic) before and after the intervention

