 - Association between mean HCW competency scores per facility and adolescent satisfaction scores
 - Associations between mean adolescent satisfaction scores and 1) retention in care (binary), 2) referral to APS services (binary), 3) ART adherence (binary or mean percent), and 4) viral suppression (binary) comparing the exposed and unexposed periods.
- Evaluation of temporal trends: Temporal trends that change over time (e.g. introduction of new HIV treatment guidelines, COVID-19) and potentially impact study outcomes can lead to a biased effect estimate in a stepped-wedge trial design [34]. To assess this possibility, we will repeat the primary analyses including an interaction term between a time indicator (e.g. coded as 'pre' versus 'post' policy/program change) and the variable for the main effect. A p-value for the interaction <0.1 will be evidence of interaction. We will report these results in a separate table showing any differences in intervention effect by this temporal change.

- Lag effects of SPEED intervention: Because the effect of the intervention may not be immediate or it may diminish over time, we will evaluate these possibilities in two ways. HCWs may take time to put skills they learned in the training into practice. In addition, trained HCWs may decrease or stop using these new skills. Intervention lag will be modeled by re-coding the first month after the intervention as a control period, as recommended by Davey *et al.* [34]. We will model the reduction of the intervention effect over time by using a fractional term for the coefficient of primary effect estimate, which will have a value of 1 (assumes 100% exposure) and get smaller at each time step (e.g. 75%, 50%, 25%).
- Qualitative analysis of exit interviews: Qualitative data from the HCW exit interviews will be coded in Atlas.ti. Data will be analyzed by two reviewers using thematic analysis according to the interview guide. These results will be utilized to complement results from the structured HCW satisfaction surveys.

Cost-effectiveness Analysis (CEA) and Cost Utility Analysis (CUA)

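### If the training effect wanes, the constant-effect estimate overstates the average effect, and the planned decay check assumes the waning instead of estimating it

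*Combined protocol and SAP*

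**What the plan says.** Section 12c (Stepped-Wedge Randomized Controlled Trial) defines exposure by intention to treat: adolescents seen at a clinic "after the SPEED training will be 'exposed' to HCWs trained in the SPEED intervention until the end of the study". For estimation, "we will use a GLMM model with a Poisson distribution and robust standard errors", with a clinic random effect, fixed time effects and one coefficient on the exposure indicator.

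Section 8 sets the timing: "Each wave will be rolled out approximately every nine months". In Table 3, wave 1 is therefore exposed in four measurement periods, wave 2 in three, wave 3 in two and wave 4 in one.

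Under Lag effects of SPEED intervention, the same section 12c gives its reason for further analysis: "Because the effect of the intervention may not be immediate or it may diminish over time". Two analyses follow. One re-codes the first month after training as control. The other multiplies the treatment coefficient by a fraction "which will have a value of 1 (assumes 100% exposure) and get smaller at each time step (e.g. 75%, 50%, 25"%).

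The plan has no effect by time since training, does not estimate the fractions, and does not say what the single risk ratio or risk difference means if the effect wanes. The interaction planned for temporal trends is with calendar time (before or after a policy or programme change), not with time since training. Section 11 repeats the health workers' self-rated competency survey ("The survey will be repeated to assess changes in competency over time during the trial") and section 7d tracks staff turnover. These describe mechanism, not how retention changes with time since training.

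**The concern.** For a one-time training, its value depends on how much of the effect lasts. If the effect fades, a reader will take the single coefficient as the average effect during the trial, but the stepped-wedge weighting pulls it towards the effect just after training. The decay analysis cannot correct this, because its answer depends on the fractions put in. Even with correct fractions, its coefficient is the full-exposure effect and must be multiplied by the mean fraction to give an average.

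Aim 3 reports cost per additional adolescent retained, and section 12c does not say which effect estimate feeds it. Too large an effect there makes the training look cheaper than it is.

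**Working it through.** **Inputs.** Section 12a: 24 clinics, 5 time points, 75% control retention, a 15-point difference (to 90%), CV 0.25, two-sided alpha 0.05. Section 8, Table 3: four waves of six clinics. Records per clinic-period: 6 (used in the 720 total) and 40 (the optimal scenario). Clinic SD τ = 0.25 × 0.75 = 0.1875, so τ² = 0.03516. Cell-mean variance σ² = 0.825 × 0.175 / n = 0.1444 / n.

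**1. The plan's own figure.** The Hussey-Hughes variance is

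Var = Iσ²(σ² + Tτ²) / [(IU − W)σ² + (U² + ITU − TW − IV)τ²],

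with I = 24, T = 5, U = 60, W = 36 + 144 + 324 + 576 = 1,080 and V = 6 × (16 + 9 + 4 + 1) = 180. The brackets are then 360σ² + 1,080τ². At n = 5 the SE is 0.0542 and power is 79.1%. At n = 6 the SE is 0.0497 and power is 85.4%. At n = 40 power exceeds 99.9%. The section 12a figures reproduce.

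**2. What the single coefficient averages.** In that model, clinic i in period j gets weight proportional to

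X_ij − X̄_j − λ(X̄_i − 0.5), with λ = Tτ² / (σ² + Tτ²).

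The share of clinics exposed by period is X̄_j = 0, 0.25, 0.5, 0.75, 1. The share of periods exposed by wave is X̄_i = 0.8, 0.6, 0.4, 0.2. Summing by step since training (per clinic in each wave) gives 1.5, 0.75 − 0.3λ, 0.25 − 0.4λ and −0.3λ, with total 2.5 − λ. Dividing by the total:

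| Setting | λ | Step 1 | Step 2 | Step 3 | Step 4 |
|---|---|---|---|---|---|
| No clinic variance | 0 | 0.60 | 0.30 | 0.10 | 0.00 |
| CV 0.25, n = 6 | 0.880 | 0.93 | 0.30 | −0.06 | −0.16 |
| CV 0.25, n = 40 | 0.980 | 0.99 | 0.30 | −0.09 | −0.19 |

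**3. Effect of waning.** Exposed clinic-periods by step number 24, 18, 12 and 6. Relative to the first-step effect:

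- Example path 1, 0.75, 0.50, 0.25. Clinic-period average: (24 + 13.5 + 6 + 1.5) / 60 = 0.75. Equal-weight average: 2.5 / 4 = 0.625. Single coefficient: (2.1875 − 0.5λ) / (2.5 − λ) = 0.875, 1.08 and 1.12 in the three settings. That is 17-49% above 0.75 and 40-79% above 0.625.
- Milder path 1, 0.9, 0.8, 0.7. Averages: 54 / 60 = 0.90 and 3.4 / 4 = 0.85. Single coefficient: (2.375 − 0.8λ) / (2.5 − λ) = 0.95 to 1.05. That is 6-16% and 12-23% above.

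For a 15-point first-step effect on the example path, the estimate is 15 × 0.875 = 13.1 to 15 × 1.117 = 16.8 points. The averages are 15 × 0.75 = 11.3 and 15 × 0.625 = 9.4.

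**4. Aim 3.** Cost per additional adolescent retained is cost divided by effect. Using the single coefficient understates it, relative to the clinic-period average, by 1 − 0.75/0.875 = 14% to 1 − 0.75/1.117 = 33%.

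**5. The fixed-fraction check**, assuming 100/75/50/25%:

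| True path | Fitted coefficient / first-step effect | × 0.75 = implied clinic-period average | Truth |
|---|---|---|---|
| 1, 0.9, 0.8, 0.7 | 0.87-0.95 | 0.66-0.71 (21-27% low) | 0.90 |
| No waning | 0.79-0.91 | 0.59-0.68 (32-41% low) | 1.00 |

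The error can also go the other way. With a true path of 1, 0.5, 0.25, 0.125 at n = 6, the implied equal-weight average is 0.635 against a true 0.469.

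**6. The planned Poisson model.** Binary outcomes were simulated on the example path and fitted with Poisson random-intercept models (log risk-ratio scale, initial risk ratio 1.10, CV 0.10 or 0.15). The single effect was 0.90-1.00 times the initial effect, which is 20-33% above 0.75 and 44-60% above 0.625. On the same data a separate-step model gave 0.71-0.77 (true 0.75) and 0.59-0.64 (true 0.625). A second set of simulations, with initial risk ratio 1.2, gave 0.88-1.05 for the single effect. CV 0.25 was not simulated at risk ratio 1.10, because the ceiling on a probability distorts the risk ratio there.

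**The case against.** The plan already names waning and pre-specifies an analysis of it. The fractions are marked as examples, and sensitivity analyses commonly work under stated assumptions. The plan also never says it will turn the decay coefficient into an average. Read as a first-step effect, that coefficient is only 5-13% low when the truth is the milder path. This stands as far as it goes. But any other preset values would equally be assumed, and a first-step effect does not answer the question of durability.

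The widest figures come from linear theory, with the top end at CV 0.25 and 40 records per cell. The Poisson simulations at risk ratio 1.10 give 0.90-1.00, or 13.5-15 points on 15, and a cost understated by 1 − 0.75/0.90 = 17% to 1 − 0.75/1.00 = 25%. That narrows the size but not the direction. The example waning is steep, and the documents hold no evidence for it. On the milder path the gap to the clinic-period average is about 1-2 points on 15. The Aim 3 consequence depends on which estimate is used.

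Precision is the most serious objection. Section 12a expects that "only a small proportion of the 40 HIV-positive adolescents enrolled in HIV care per clinic may be newly enrolled" or recently re-engaged, so cells may be small. This is a reason to keep the step model secondary and to read it through its interval. It is not a reason to rely on assumed fractions.

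**Conclusion.** The concern holds. If the effect wanes with time since training, the planned single estimate lies near the first-step effect and above either average, in every clinic-variance setting tried. Under the plan's example fractions the excess over the clinic-period average is 17-49% by linear theory and 20-33% in the Poisson simulations at risk ratio 1.10. Under the milder path it is 6-16%. The decay analysis cannot show whether waning occurred, because it does not estimate the fractions.

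The size rests on an assumed waning path and clinic variance, additive period effects and equal cell sizes. With no waning there is no bias. With no effect at any step the estimate is centred on zero, so the test of no effect is not biased by this. The change should be made, but it concerns the size and meaning of the reported effect, not the validity of the primary test.

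**What to change.** Keep the primary model, its test and the one-month lag analysis. In section 12c, replace the fixed-fraction decay analysis with a pre-specified secondary model: a separate effect for each nine-month step since training (1 to 4), with the same period effects and clinic random intercept. Report the four effects and the exposed clinic-period average, with the equal-weight average alongside, all with confidence intervals, next to the constant-effect estimate. Use the clinic-period average and its interval as a sensitivity input to Aim 3 and for any statement about durability.

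State that step 4 is seen only in wave 1 in the last period, when no clinic is untreated. Pandemic disruption may overlap with that period (section 7a: "Due to COVID-19 pandemic starting March 2020, HCW surveys for Wave 4 will be conducted by phone"). Step 4 therefore rests on the additive model and needs cautious reading.

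The change needs SAP wording and no new data. The cost is precision. At CV 0.25 the SE is 1.25-1.35 times larger for the clinic-period average and 1.45-1.6 times for the equal-weight average. Power for a 15-point average effect (ranges span residual variance 0.825 × 0.175 and 0.75 × 0.25):

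| Records | Single effect | Clinic-period average | Equal-weight average |
|---|---|---|---|
| 24 clinics, 6 per cell | 76-85% | 57-66% | 45-53% |
| 20 clinics, 7 per cell | 75-84% | 55-64% | 43-51% |
| 24 clinics, 40 per cell | >99% | about 99% or more | about 99% or more |

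If a 15-point initial effect wanes by the example fractions, power at 6 per cell falls to 36-43% (clinic-period) and 21-25% (equal-weight), and the step-4 SE is 0.12-0.14. At the minimum size the average should be read as an estimate with its interval, not as a test.

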For the stepped-wedge randomized controlled trial, the 24 clinics will be randomized to *the time* when they receive the SPEED intervention. In this one-way cross-over design, all 24 sites will eventually receive the intervention. Groups of 6 clinics will be randomized to receive the intervention in one of four waves. We will use stratified randomization where facilities are also allocated to waves according to region and by facility size, defined as 'high volume', more than 73 AYA enrolled and medium volume, 73 or fewer AYA enrolled, based on the median, to ensure balance of characteristics in each wave [31]. A UW Biostatistician will generate the randomization assignment for each clinic in R Statistical Software (R Core Team, Vienna, Austria).

5g. Masking procedures

Because this a clinic training intervention using a pragmatic trial design, there will be no masking procedures.

5h. Participant Withdrawal

Participants may withdraw from the study at any time or the investigator may terminate a participant's participation.

Reasons for Withdrawal

Reasons for a study clinic to withdraw may include: clinic closure or major changes in HIV testing and treatment policies, procedures, or organization structural that would prevent or substantially limit our ability to conduct this study.

Reasons for HCW participant withdrawal may include: discomfort or distress as a result of the training, lack of time to complete the follow-up surveys, or job termination or relocation.

Reasons for an adolescent participant to not complete the satisfaction survey may include, lack of time, comfort, or interest in answering the questions.

An investigator may terminate a study participant's involvement in the study if **any medical condition or situation occurs such that continued participation in the study would not be in the best interest of the participant; or if** a HCW participant behaves in a way that disrupts or prevents the successful conduct of the SP encounter training.

Handling of participant withdrawals

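### The primary analysis uses robust standard errors from 24 clinics with no small-sample correction or reference distribution; with a normal reference, the 5% test runs at about 7–8%

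*Combined protocol and SAP*

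**What the plan says.** Section 12c (Stepped-Wedge Randomized Controlled Trial) gives the model: "we will use a GLMM model with a Poisson distribution and robust standard errors", "allowing for random effects for clusters" and with fixed effects for time. It says that this approach "accounts for correlation of outcomes within a cluster (clinic"). On inference it says: "We will estimate adjusted risk ratios (ARR), adjusted risk differences (ARDs) and 95% confidence intervals at the 5% significance level (two-sided").

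Section 5f sets the unit of randomisation: "Groups of 6 clinics will be randomized to receive the intervention in one of four waves". Section 12a explains the number of clinics: "We include 24 clinics in this study to account for the possibility that 15% drop-out without replacement". For the case where 20 remain, it says "we would need 7 adolescents per site, per time point, or a minimum of 700 records total".

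The supplied text does not say how the robust variance is corrected for few clinics, which distribution the test statistic is referred to, or whether a permutation test will be used.

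**The concern.** A robust (sandwich) variance is justified by a large number of independent clusters. With 20 to 24 clinics it is biased downward and is itself variable, so a normal reference gives intervals that are too narrow and too many false positives.

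This matters more than usual here because the robust standard error carries the test. Retention is binary, and the planned Poisson model overstates its variance: at 75% retention a Poisson variance is 0.75, against 0.75 × 0.25 = 0.1875 for a binary outcome. In simulation the model-based standard error rejected a true null in under 1% of trials. Whether the stated 5% level holds therefore depends on how the sandwich is computed and referenced. The plan leaves that open, so the choice could be made after the data are seen and could move a borderline result.

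**Working it through.** **Inputs.** From section 12a: control retention 0.75; between-clinic coefficient of variation 0.25, so τ = 0.25 × 0.75 = 0.1875; a 15% difference, read as 75% to 90%; two-sided α = 0.05; 5 time points; 24 clinics with 6 records per clinic-period, 20 with 7, or 40 records in the optimal case. Sections 5f and 8 give four waves of 6 clinics.

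**Step 1: reproduce the plan's sample size.** The Hussey–Hughes variance is

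Var = Iσ²(σ² + Tτ²) / [(IU − W)σ² + (U² + ITU − TW − IV)τ²],

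where I is clinics, T is periods, U is the number of exposed clinic-periods, and W and V are the sums of squared exposed counts by period and by clinic. Take σ² = 0.825 × 0.175 / n = 0.144375 / n.

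- 24 × 6: U = 60, W = 1080, V = 180, σ² = 0.02406. Var = 0.11541 / (360 × 0.02406 + 1080 × 0.03516) = 0.11541 / 46.631 = 0.002475. SE = 0.0497; 0.15 / 0.0497 = 3.015; power = Φ(3.015 − 1.960) = 85.4%. Five records give 79.1%, so 6 are needed: 6 × 24 × 5 = 720, as stated.
- 20 × 7: U = 50, W = 750, V = 150, σ² = 0.02063. Var = 0.08102 / 31.523 = 0.002570. SE = 0.0507; power = Φ(2.959 − 1.960) = 84.1%. Six records give 78.6%, so 7 are needed: 7 × 20 × 5 = 700, as stated.
- At 40 records power exceeds 99%, as stated.

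The inputs are therefore read as the plan intends.

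**Step 2: simulate the planned test with no intervention effect.** Binary outcomes were generated with beta clinic proportions (mean 0.75, SD 0.1875), equal clinic sizes, equal waves, no covariates and no time or treatment effect. Each dataset was fitted as a random-intercept Poisson GLMM with period effects, with a clinic-level sandwich on all parameters. There were 30,000 trials per setting (Monte Carlo SE about 0.15 point). The table shows rejections at nominal 5%, with G the number of clinics:

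| Clinics × records | Uncorrected, normal | G/(G−1), normal | G/(G−1), t(G−2) | Kauermann–Carroll, t(G−2) |
|---|---|---|---|---|
| 24 × 6 | 7.4% | 6.9% | 5.5% | 4.6% |
| 24 × 40 | 7.3% | 6.6% | 5.3% | 4.6% |
| 20 × 7 | 8.2% | 7.6% | 5.8% | 4.6% |
| 20 × 40 | 7.7% | 7.1% | 5.3% | 4.5% |

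Uncorrected risk-difference intervals with a normal reference missed zero in 7.7–8.9% of null trials. At 24 × 6 and 20 × 7, 19% and 15% of fits had near-zero clinic variance; the variance was treated as fixed in those fits.

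**Step 3: see where the excess comes from.** At 24 × 40 the uncorrected robust SE averaged 0.0283 against a true SD of 0.0303, a ratio of 0.934. At 20 × 40 it was 0.0308 against 0.0335, a ratio of 0.919. That bias alone gives 2[1 − Φ(1.96 × 0.934)] = 6.7% and 2[1 − Φ(1.96 × 0.919)] = 7.2%. Most of the rest, up to 7.3% and 7.7%, is what one expects when an estimated SE is referred to a normal distribution. The excess remains at 40 records because the limit is the number of clinics.

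**Step 4: check stability.** Separately coded fits of the same GLMM gave 7.0–8.2% uncorrected with a normal reference, and 6.5–7.4% with G/(G−1). Two related estimators that section 12c does not name (a fixed-effects-only sandwich and an exchangeable Poisson GEE), together with truncated-normal and capped-gamma clinic effects and 20 clinics left as 6/6/4/4, widen the four columns to 6.6–8.6%, 6.1–8.0%, 4.8–6.0% and 4.2–5.4%. One run with a gamma-shaped effect gave 5.4% at 24 clinics; another, with G/(G−1) and a normal reference, gave 6.4–6.7%.

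**The case against.** The strongest reply is that this is an omission from a section headed as an overview, not a wrong statement. The plan never says that a normal reference will be used. An analyst who scaled by G/(G−1) and used a t reference would be at about 4.8–6.0%. That stands: every inflated figure is conditional on a normal reference. It does not dispose of the point, because the text as written allows either choice, and the usual application gives intervals that are too narrow.

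The excess is also modest, and the documents give only the mean and coefficient of variation of the clinic effect. The beta shape, equal sizes and absence of covariates are assumptions made here. That also stands.

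A reader might infer that the planned covariates and unequal clinic sizes make matters clearly worse. The documents do not support a figure for this: they give no covariate coding and no spread of analysed records. With three assumed binary clinic covariates, uncorrected GLMM runs gave 9.0% (24 × 6), 7.8% (24 × 40) and about 10% (20 × 7), but GEE runs gave 6.9%, 7.2% and 7.6%, with no clear penalty. An assumed size spread (log-SD 0.6) gave 8.9% at 24 × 6 and 7.5% at 24 × 40.

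Finally, correction costs power where the plan has little to spare. This is true, but an inflated error rate is not a legitimate source of power.

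**Conclusion.** The concern holds as a gap in specification with a modest, conditional consequence. With a normal reference, the planned full-parameter sandwich runs at about 7–8% (6.6–7.6% with G/(G−1)) against a stated 5%. This rests on the protocol's inputs plus a beta clinic effect, equal sizes and no covariates. Confidence is high that the method is unspecified and that the error is above 5% under a normal reference; it is lower for the exact size.

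Two stronger readings should be avoided. The documents do not show that the trial will be analysed at 8%, since no reference distribution is stated. Nor do they support treating this as a flaw in one single confirmatory comparison: section 3a lists two retention definitions under the primary outcome (return after an enrolment or re-engagement visit, and return within 3 months among those actively enrolled), while the model sentence in section 12c names only the first. The remedy has to cover both. It is worth fixing before analysis; it is not a fault in the design.

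**What to change.** Before analysis, add to section 12c a Kauermann–Carroll-type corrected clinic-level sandwich with a t reference on clinics minus 2 degrees of freedom. Apply it to the test and to both the risk-ratio and risk-difference intervals, for each primary retention definition in section 3a. Its level was 4.2–5.4% across all the no-covariate settings above (4.7–5.2% for the risk difference). At minimum, use G/(G−1) with the same t reference (4.8–6.0%). Once covariate coding and clinic sizes are fixed, the chosen method should be checked on that model. With the assumed covariates, the minimum option still ran at 6.7% (24 × 6) and 7.5% (20 × 7) in the GLMM. The Kauermann–Carroll version held 4.3–4.6% with covariates, but was tested there only in a GEE.

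A permutation test that re-randomises clinics to waves within the section 5f strata is an alternative for the p-value. It does not by itself supply the promised intervals, and it was not simulated because stratum sizes are not given.

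**Cost.** The change needs SAP wording and a short routine; design and data are unchanged.

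- *Width.* Kauermann–Carroll with t gives intervals 10–16% wider than uncorrected with normal. The minimum option is 8–10% wider: (2.074 / 1.960) × √(24/23) = 1.08 and (2.101 / 1.960) × √(20/19) = 1.10.
- *Power by the plan's formula.* The t reference alone takes it from 85% to 82% (24 × 6) and from 84% to 80% (20 × 7).
- *Power in the simulated GLMM* (assumed common logit shift from 75% to 90%). It falls from 68% to 59% (24 × 6) and from 64% to 52% (20 × 7), so even the uncorrected test is below 80% at the 720- and 700-record minimum. The corrected test reaches about 80% at 12 records per clinic-period with 24 clinics and at 16 with 20 clinics. At 40 records it keeps about 99% or more.
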